4.1 Screening Procedures

Patients will be screened against the inclusion and exclusion criteria on admission to ICU.

4.2 Consent and Enrolment Procedures

Critically ill patients often have impaired capacity as a result of their underlying illness and/or sedating medications. Therefore, there will be three routes by which a patient may be enrolled in the study.

i) Patient with capacity to consent:

- The patient will be provided with a written 'Patient Information Sheet'.
- A member of the research team with a valid GCP certificate will provide verbal information and answer any questions.
- If the patient chooses to be enrolled in the study they will be asked to sign a 'Patient Consent Form'.
- The patient may withdraw consent at any stage (as explicitly stated in the 'Patient Information Sheet').

ii) Patient without capacity where a Personal Consultee is immediately available:

- When a patient does not have capacity, the research team will attempt to identify a personal consultee (in accordance with section 32 of the mental capacity act).
- The personal consultee will be provided with a written 'Personal Consultee Information Sheet'.
- A member of the research team with a valid GCP certificate will provide verbal information and answer any questions.
- The personal consultee will be asked to use their knowledge of the patient's beliefs to advise the research team as to whether or not they feel the patient would chose to enrol in the study.
- When the personal consultee feels the patient would have chosen to participate in the study they will be asked to sign a 'Personal Consultee Declaration Form'.
- If the Personal Consultee is unable to come to the hospital, we plan to contact them by phone. We will provide information about the study and email or fax the "Personal Consultee Information Sheet" and answer any questions. If the personal consultee feels the patient would have chosen to participate in the study, we will email or fax a 'Personal Consultee Declaration Form' and ask them to sign and send it back to us.

- The personal consultee may withdraw the patient at any stage (as explicitly stated in the 'Personal Consultee Information Sheet').
 - When the patient regains capacity, the research team will speak to the patient at the earliest opportunity and ask the patient to provide consent to continue participation; if the patient chooses to continue to participate in the study they will be asked to sign a 'Consent Form (Continuation)'; if the patient gives consent, they are free to withdraw their consent at any time; if the patient does not wish to consent, they will be withdrawn from the study.
 - In the event that the patient never regains capacity or dies then he/she will remain in the study and their data will be included in the final analysis.
- iii) Patient without capacity where a Personal Consultee is not immediately available:
- When a patient does not have capacity and the research team are unable to identify or contact an appropriate personal consultee we will contact a Nominated Consultee.
 - The nominated consultee will be a Consultant Intensivist who understands the patient's medical problems and has been informed about the study. The nominated Consultee may be the Consultant who is caring for the patient or a Consultant who is not directly involved in the clinical care of the patient. All Consultants who agree to act as nominated consultees will be listed in the site file.
 - The nominated consultee will not be a member of the study team and will have no connection to the research, to the funder or to the Research Ethics Committee.
 - The nominated consultee will be provided with a 'Nominated Consultee Information Sheet' and a member of the research team with a valid GCP certificate will provide verbal information and answer any questions.
 - When the nominated consultee finds no reason why the patient would not have chosen to enrol in the study they will be asked to sign a 'Nominated Consultee Declaration Form'.
 - The nominated consultee may request at any stage that the patient is withdrawn (as explicitly stated in the 'Nominated Consultee Information Sheet').
 - When the patient regains capacity, the research team will speak to the patient at the earliest opportunity and ask the patient to provide consent to continue participation; if the patient chooses to continue to participate in the study they will be asked to sign a 'Consent Form (Continuation)'; if the patient gives consent, they are free to withdraw their consent at any time; if the patient does not wish to consent, they will be withdrawn from the study.
 - In the event that the patient never regains capacity or dies then he/she will remain in the study and their data will be included in the analysis.

We will record all ECG data from admission. If a patient or consultee declines consent, the patient will be removed from the study and all data obtained so far will be destroyed. Patients, personal consultees and nominated consultees will be given 24 hours to make a decision regarding participation in the study. If patients or their personal consultees need longer to make an informed decision, this will be respected and facilitated if possible.

In situations where the personal consultee is not able to come to the hospital, we also plan to take informed consent over the phone. In this case, a member of the research team will contact the personal consultee and inform them about the study. They will be sent an information sheet by email or fax as preferred. The personal consultee will be given adequate time and opportunities to ask questions over the phone. If they agree that they are not aware of any reasons why the patient may not have wanted to participate, they will be asked to sign the declaration form and return it to the research team by email, Royal Mail or in person. When the patient regains capacity, the research team will speak to the patient at the earliest opportunity and ask the patient to provide consent to continue participation; if the patient chooses to continue to participate in the study they will be asked to sign a 'Consent Form (Continuation)'; if the patient gives consent, they are free to withdraw their consent at any time; if the patient does not wish to consent, they will be withdrawn from the study.

4.3 Schedule of study procedure

With informed consent, the following routinely recorded clinical and laboratory data will be collected:

- Baseline demographics and comorbidities
- Administration of beta blockers or anti-arrhythmics
- Administration of sedative agents (general anaesthetics/opioids/benzodiazepines)
- Reasons for admission to ICU
- Daily biochemistry and haematology results
- Severity of illness scores, including APACHE II and daily SOFA scores
- Daily CAM ICU scores / delirium
- Daily cardiac rhythm as per nursing entry or clinical diagnosis
- Daily clinical parameters, including medications (vasopressors/ionotropes/steroids/muscle relaxants) and organ support
- Daily AKI stage, including treatment with RRT

After obtaining informed consent, continuous ECG data will be recorded using the two different devices. ECG data will then be processed to derive HRV using the methodology described by the European Society of Cardiology Taskforce guidelines.² Processing of ECG data entails checking

for and removal of extrasystole and ectopic beats with interpolation of QRS complexes as described elsewhere.² Continuous 24 hour ECG recording will then be divided into 5 minute epochs for which short term HRV values will be calculated. HRV will be calculated in the time domain, frequency domain and non-linear domains for each 5 minute epoch. Entire 24 hour ECG recordings will be used for long term HRV measures in the time domain, frequency domain and non-linear domains as described the Taskforce guidelines.² HRV data will then be analysed according to that described in the statistical methodology and analysis section. HRV data will be calculated by the Medical Engineering and Clinical Physics department at the Royal Liverpool and Broadgreen University Hospital. They will be blinded to any patient identifiable or clinical information.

Daily data will be collected until day 5 in ICU, day of discharge from ICU or day of death (depending on what occurs first). In addition, we will record ICU and hospital length of stay, ICU and hospital mortality and occurrence of arrhythmias during ICU stay, after 30 days, and after 90 days following enrollment. Data will be collected by accessing routinely available results in the patients' medical records, and if necessary, by contacting the patient's General Practitioner (GP).

There will be no change in clinical practice. Patients will not receive any therapies or interventions that they would not have received if they had not been enrolled in the study and no tissue samples will be taken.

After a participant's discharge from the ICU, the medical and nursing staff involved in the care will be asked to fill in a questionnaire to evaluate userfriendliness, interference of HRV monitoring systems with routine medical and nursing procedures and their views on using such devices in a larger clinical trial. With informed consent from the staff member, the responses will be collected and analysed.

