Chief Investigator	[name]. med. [name]
REC number	
Medical condition under investigation	Critical illness
Purpose of clinical trial	To investigate if two devices to monitor and capture Heart Rate Variability (HRV) and ECG data in Critically ill patients produce comparable results.
Primary objective	To describe the robustness of data on HRV obtained by two different monitoring systems during daily care of critically ill patients.
Secondary objective	
 1. To identify the most suitable and cost-efficient device for HRV monitoring in critically ill patients. 2. To define amendments in data capture and analysis required to proceed to a larger clinical trial
Number of Subjects	30 patients

Trial Design	Prospective observational feasibility study
Endpoints	
Primary outcome:
 
 • Number of interpretable HRV epoch episodes for each device and comparison between Isansys device and gold-standard holter monitoring (Isansys and Holter Monitor) 
Secondary outcomes:
 
 • Correlation of HRV time domain, frequency domain and non-linear HRV measures analysis between Isansys wireless monitoring patch and Holter monitoring • Correlation between HRV and onset of arrhythmias • Correlation between HRV and cardiorespiratory events (desaturation, drop in blood pressure >20%, change in ventilator settings) • Nurses' and medical staff's perception of the usability of both monitoring systems in daily routine practice
Main inclusion and Exclusion Criteria	
Inclusion criteria:
 
 • Adult patients ≥18 years • Expected stay in the ICU >48 hours • Sinus rhythm on ITU admission • Mechanically ventilated patients 
Exclusion criteria:
 
 • Non-ICU patient • History of Atrial Fibrillation • Inability to obtain consent
Randomization	Not applicable
Study procedure	
If all inclusion criteria are met and no exclusion criteria are present, patients will be eligible, invited to participate and informed consent will be sought.
 
Continuous ECG data will be recorded using two different devices. ECG data will then be processed to derive HRV using the methodology

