2.1 Trial objectives

The **primary objective** is:

- To describe the robustness of data on HRV data obtained by two different monitoring systems in daily care of critically ill patients. The Isansys wireless monitoring device will be compared to the gold-standard holter monitoring device for ECG analysis.

The **secondary objectives** are:

- To identify the most suitable and cost-efficient device for HRV monitoring in critically ill patients.
- To define amendments in data capture and analysis required to proceed to a larger clinical trial
- To generate preliminary data on the variation of HRV in a critical care patients.

Primary outcome:

- Number of interpretable monitoring epochs in each HRV monitoring system after elimination of artefacts, extra beats and interference

Secondary outcomes:

- Correlation and comparison of HRV time, frequency and non-linear measures between the Isansys monitoring device and the gold-standard holter monitoring system.
- Correlation between HRV and onset of arrhythmias (ventricular or atrial)
- Correlation between HRV and cardiorespiratory events that commonly occur in critically ill patients, including, oxygen desaturation (SaO₂<85%), variations in blood pressure of >20%, change in ventilatory support, muscle paralysis, position of the patient, administration of vasopressors (e.g. noradrenaline and vasopressin).
- Nurses' and medical staff's perception of the usability of both monitoring systems in daily routine

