3.1 Sample size

In this single-centre study we wish to analyse 40 consecutive patients in whom a complete set of data can be obtained. From our previous experiences the incidence of AF in our intensive care unit is approximately 13.8%. Therefore in a sample size of 40 patients we would expect 2-3 patients to develop AF. This would allow us the opportunity to investigate any correlation between the changes in HRV preceding the onset of AF and investigate our secondary objectives to inform a larger clinical trial.

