4.5 End of Study Definition

The study will end after a total of 30 evaluable patients with complete data collection have been enrolled.

5. Laboratories

Not applicable

6. Assessment of Safety

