6.2 Safety of Heart rate variability monitoring devices

Device 1

Isansys Lifetouch Sensor is a fully CE marked medical device. The monitoring system includes single use wearable adhesive patches which are supplied in at least three sizes, depending on the age and size of the patient. Each Lifetouch provides the following clinical data continuously for a period of up to 5 days:

- Heart rate
- Respiration rate
- Real time heart rate variability
- Visualization of the ECG
- 3 axes accelerometer output

The Isansys Lifetouch Sensor is fully wireless and battery operated. The battery is not accessible to the patient or staff. All Isansys Lifetouch Sensor are single patient use and will be disposed off by following local procedures Information is transmitted wirelessly to a mobile patient status engine (ipad) via wifi and Low energy Bluetooth connectivity. The patient status engine Gateway is supplied in a protective medical grade bezel frame sealed in such a way to allow it to be cleaned with standard disinfecting/sterilising liquids or wipes. The device is safe with all other intensive care monitoring.

Device 2

Ambulatory Holter ECG monitoring is a standard of care used by the cardiorespiratory department. Ambulatory holter monitoring involves attaching a 12 lead ECG to the patient in the standard ECG lead configuration using standard ECG adhesive dots. Holter monitors record continuously for 72 hours onto a memory card and are entirely battery operated with no new electrical connection to the patient. Following 72 hours the memory card is analysed using software provided by the holter monitoring company. The software is of medical standard and provides HRV data, data on the number of interpretable episodes, data on ectopic beats and arrhythmias. Ambulatory holter monitoring is already in routine clinical use within the Royal Liverpool and Broadgreen University Hospital. They are CE marked and validate for use on patients.

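### The HRV–arrhythmia outcome needs a timed onset, but section 4.3 takes rhythm from a daily chart entry and no section assigns the Holter's own arrhythmia output to it

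*Protocol*

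**What the plan says.** **Outcome.** The protocol synopsis lists "Correlation between HRV and onset of arrhythmias" as a secondary outcome. Section 2.1 lists the same outcome and specifies that both ventricular and atrial arrhythmias count.

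**HRV scale.** Section 4.3 divides each 24-hour recording into 5-minute epochs for the short-term measures. Whole 24-hour recordings serve the long-term measures.

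**Rhythm and arrhythmia data.** Among the routinely recorded items, section 4.3 lists "Daily cardiac rhythm as per nursing entry or clinical diagnosis". It separately records whether arrhythmias occurred during the ICU stay and at 30 and 90 days, from medical records and, if needed, the GP.

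**Holter.** Section 6.2 describes a continuous 72-hour recording, analysed after it ends with software that "provides HRV data, data on the number of interpretable episodes, data on ectopic beats and arrhythmias". The arrhythmia outcome is not mentioned there, and the Holter output is not mentioned as a source of arrhythmia events in sections 2.1, 2.3 or 4.3.

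**Planning.** Section 3.1 says that "the incidence of AF in our intensive care unit is approximately 13.8" per cent and that "we wish to analyse 40 consecutive patients in whom a complete set of data can be obtained". It expects two to three of them to develop AF, which is to give an opportunity to "investigate any correlation between the changes in HRV preceding the onset of AF" and to pursue the secondary objectives. Section 4.5, however, says: "The study will end after a total of 30 evaluable patients with complete data collection have been enrolled".

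**The concern.** An analysis of HRV in relation to onset needs two things per patient: whether an arrhythmia occurred, and when it began relative to the HRV series. The only sources that section 4.3 names for rhythm are chart-based. A daily entry can give an approximate answer to the first question and cannot answer the second on the scale at which HRV is measured. Brief episodes that nobody charted would not appear at all.

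At stake is a pilot result meant to inform a larger trial. If event patients are placed in the no-event group for reasons unrelated to their HRV, the observed association tends to weaken. If onset is dated to a day, epochs from after onset can be treated as epochs before it. The larger trial would also inherit an event rate that depends on charting. All this would happen while a continuous ECG with a software arrhythmia report is available for the same patients.

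**Working it through.** **1. Time resolution.** Inputs: 5-minute epochs (4.3), a daily rhythm entry (4.3), a 72-hour Holter recording (6.2).

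- Epochs per day: 24 × 60 / 5 = 288.
- Epochs in the Holter recording: 72 × 60 / 5 = 864.

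A change from sinus rhythm to arrhythmia between two daily entries places the onset only within a window of about 288 epochs. A clinical diagnosis in the notes may carry a clock time, but section 4.3 does not ask for one, and it would mark recognition, not onset.

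**2. Windows.**

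| Item | Covers | Section |
|---|---|---|
| Holter ECG and its arrhythmia report | 72 hours | 6.2 |
| Isansys patch | up to 5 days; no arrhythmia report among its listed outputs | 6.2 |
| Daily rhythm entry | to day 5, ICU discharge or death | 4.3 (synopsis: day 14) |
| Arrhythmia occurrence | ICU stay, 30 and 90 days | 4.3 |

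An arrhythmia first noted at day 30 or 90 has no concurrent HRV recording. No section says which window supplies the events for the correlation.

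**3. The plan's own AF figure.** Expected cases = N × incidence.

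- N = 40 (3.1): 40 × 0.138 = 5.52, against two to three stated. Not reproduced.
- N = 30 (synopsis, 4.5): 30 × 0.138 = 4.14. Also above the stated range.
- Incidence implied by the stated count in 40: 2/40 = 5.0% to 3/40 = 7.5%.
- Patients for whom two to three cases would be expected at 13.8%: 2/0.138 = 14.5 to 3/0.138 = 21.7.
- Exact binomial probability of three or fewer cases at 13.8%: 0.18 for N = 40 and 0.39 for N = 30.

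Seeing two or three cases would therefore not be surprising, but it is not the expectation that the stated inputs give. Patients with known AF are excluded, which might justify a lower rate, but section 3.1 does not say that it made such an adjustment.

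**4. Coverage of the outcome.** The protocol gives no incidence for ventricular arrhythmias or for atrial arrhythmias other than AF, so the expected number of section 2.1 events cannot be computed. Purely as an illustration, an assumed 20–40% would give 8–16 events in 40 patients or 6–12 in 30.

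**5. Sensitivity to one missed patient.** This needs no assumed capture rate. One missed AF patient is 1/5.52 = 18% of expected AF cases for N = 40, and 1/4.14 = 24% for N = 30. On the protocol's own two to three cases it is 33% to 50%. How many would be missed is not known.

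**The case against.** The defence has several fair points. The daily rhythm item sits in a list of routine data and is not labelled as the rule for deciding the arrhythmia outcome. Nothing in the protocol excludes the Holter output, and the order of precedence among sources could be set in a statistical analysis plan that is not shown. With about four to six AF cases expected, no association will be estimated well under any source. This is also a secondary outcome of a pilot whose primary outcome is the number of interpretable epochs.

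These points limit the weight of the finding but do not remove it. The source that section 4.3 does state does not fit an onset outcome, and an analysis plan cannot recover onset times from a daily entry. The choice of source belongs where data collection is fixed.

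Three stronger readings are tempting but not supported:

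- **Two rival outcomes.** A reader might infer that section 3.1 restricts the outcome to AF while section 2.1 counts all arrhythmias. It does not. The synopsis and 2.1 agree, 3.1 uses AF as a planning event and goes on to the secondary objectives, and AF is itself an atrial arrhythmia. No patient changes status by following one section instead of the other.
- **Ectopic beats making nearly everyone an event.** Section 6.2 lists ectopic beats apart from arrhythmias, and sections 2.3 and 4.3 remove them in preprocessing. Nothing suggests that an isolated ectopic counts as an arrhythmia onset.
- **A fixed misclassification percentage.** The documents give no charting sensitivity, so any percentage only restates an assumption. The 13.8% may itself come from charted cases, and discounting it again would count the same loss twice.

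**Conclusion.** The point holds as a mismatch between outcome and data source, and it is modest in weight. The outcome requires the timing of onset against 5-minute epochs. The sources named in section 4.3 resolve it to about a day (288 epochs) or, for later events, not against any recording. The Holter report could supply both presence and timing for 72 hours, but the protocol never assigns it to this outcome.

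The size of any bias is unknown. Weakening of the association is the expected direction only if missed episodes are unrelated to HRV, which the protocol gives no means to check. With 4.1 to 5.5 AF cases expected at the stated incidence, a single missed patient matters.

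Two further statements about section 3.1 stand on arithmetic and reading alone: two to three cases do not follow from 13.8% of 40, and an AF-only projection does not cover the wider section 2.1 outcome.

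**What to change.** - **Source (2.1 and 4.3).** State that, for the HRV–arrhythmia correlation, both presence and onset time come from the Holter arrhythmia output while it is worn. State that isolated ectopic beats, which preprocessing removes, are not events.
- **Window.** Limit that correlation to arrhythmias with onset during the ECG recording. Report chart-only events, and later events from the ICU stay and at 30 and 90 days, separately and labelled as such. This includes events after the Holter stops while the patch may still be recording.
- **AF.** Report AF separately within the section 2.1 outcome, so that the result can be set against section 3.1.
- **Section 3.1.** Reconcile the 13.8%, the number of patients (40 or 30) and the expected count. Say plainly that the projection concerns AF and not all section 2.1 events.

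The cost is some wording and a short review of Holter output per patient, using a report that the software already produces. One drawback remains: the method of detection changes after 72 hours. Separate reporting does not remove that change, but it makes it visible.

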The European society of cardiology guidelines recognised a number of different HRV measures. Time domain measures are the simplest method of analysis of HRV. In a continuous ECG recording, the time between adjacent R wave peaks of QRS complexes is detected. This time interval is termed the N-N interval. Simple statistical tests are then applied to the N-N interval to determine the HRV, these include the standard deviation of the N-N interval (SDNN), square root of the mean squared differences of the N-N interval (RMSSD), the number of interval differences of successive N-N intervals greater than 50ms (NN50), and the proportion derived by dividing NN50 by the total number of NN intervals (pNN50).² Frequency domain measures

make use of power spectral density analysis and fast fourier transform analysis to provide information on how power distributes as a function of frequency.² This technique splits the ECG waveform into small subunits/epochs of time depending upon whether high frequency, low frequency or very low frequency measures are required (see below). The epochs of ECG waveform recording is then transformed from a temporal signal into a spectral representation whereby ECG signal is expressed as the sum of multiple sinusoidal waves of a given amplitude and frequency. These amplitudes are then plotted to give the power spectrum by plotting power versus frequency. Spectral components include frequencies measured HF domain(0.15-0.4Hz) thought to represent the parasympathetic input, LF domain (0.04-0.15Hz) thought to represent the sympathetic nervous system and the parasympathetic nervous system, VLF domain (<0.04Hz) and the ultra-low frequency (ULF) domains (<0.003Hz).²⁷ Measurement of the frequencies can be made in absolute values, but are often recorded as normalised units which represents the relative value of each power component in proportion to the total power minus the VLF component.⁸² Non-linear methods include measures such as the Poincare plot.² In the Poincare plot an individual's N-N interval is plotted against time and standard deviation used to interpret changes.⁹ The Poincare plot is described by two descriptors, SD1 is the fast beat-to-beat variability in the R-R intervals whilst SD2 describes the longer variability.^{9,2} SD1 reflects mainly the parasympathetic component of the autonomic nervous system, whilst SD2 reflects the parasympathetic and sympathetic components.⁹

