2.3 Trial Statistics

ECG data will be downloaded from the holter device and analysis in holter device software package which derive HRV data. RR interval data from the Isansys patch will be downloaded onto an Excel spreadsheet. The RR interval will be uploaded to Matlab. The Medical Engineering and Clinical Physics department have developed a program in the Matlab environment for analysis and output of HRV data. ECG data will undergo preprocessing to remove artefacts and ectopic beats and be analysed using the Ornstein-Uhlenbeck third-order Gaussian process applied to the heart rate/RR interval.¹¹ This technique has been developed by the Medical Engineering and Clinical Physics department. Once the ECG has been preprocessed heart rate variability will be derived according to the European Society of Cardiology guidelines.²

We will use time domain measures, frequency domain measures and non-linear measures such as the poincare plot, approximate and sample entropy and detrended fluctuation analysis in our analysis of HRV.

Comparison between devices will be assessed by Bland-Altman methodology. The difference between measures recorded from the Holter monitor and the Isansys wireless monitor will be plotted against the average value for each HRV measure for individual patients. Any measure of relationship between the measurement error and the estimate of the true value (average of the two measurements) can be examined. If the difference between the Isansys monitor and the holter monitor is sufficiently small not to cause problems in the clinical interpretation (within 95% limits of agreement), then the Isansys wireless device can be considered to be interchangeable with the gold-standard holter monitoring device.

Heart rate variability data will be analysed statistically as described. Descriptive statistics showing means \pm standard deviation (SD) for continuously distributed variables, and number and proportions for categorical variables will be used for all comparisons. Chi-square tests will be used for categorical outcomes unless assumptions of the test are found to have been violated, in which case Fisher's exact test will be used.

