Appendix 1: Analysis of HRV variables

Parameter	Units	Description	Normal range
SDNN	ms	Standard deviation of the NN intervals	101.19
SDANN	ms	Standard deviation of average NN intervals	41.47
pNN50	%	Percentage of successive RR intervals that differ by more than 50ms	18.80
RMSSD	ms	Root mean square of successive RR interval differences	0.08
LF power	ms ²	Absolute power of the low frequency band (0.04 – 0.15Hz)	2534.91
HF power	ms ²	Absolute power of the high frequency band (0.15 – 0.4Hz)	2592.32
VLF power	ms ²	Absolute power of the very low frequency band (0.033 – 0.04Hz)	8307.38
LF/HF ratio	%	Ration of LF to HF power	128.78
SD1	ms	Poincre plot standard deviation perpendicular to the line of identity	57.01
SD2	ms	Poincre plot standard deviation along the line of identity	134.13
SD1/SD2 ratio	%	Ratio of SD1 to SD2	2.49

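### Approximate entropy on fixed 5-minute epochs varies with the number of beats, so its secondary correlations with clinical events could reflect heart rate alone; the VLF band also needs reconciling

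*Protocol*

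**What the plan says.** Section 4.3 of the protocol sets two analysis windows. The 24-hour recording is "divided into 5 minute epochs for which short term HRV values will be calculated", and "HRV will be calculated in the time domain, frequency domain and non-linear domains for each 5 minute epoch". Separately, "Entire 24 hour ECG recordings will be used for long term HRV measures in the time domain, frequency domain and non-linear domains". The synopsis makes the same split.

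Section 2.3 plans "non-linear measures such as the poincare plot, approximate and sample entropy and detrended fluctuation analysis in our analysis of HRV". It ties none of these to one window and sets no number of beats.

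On frequency bands, section 1 says of spectral analysis that "This technique splits the ECG waveform into small subunits/epochs of time depending upon whether high frequency, low frequency or very low frequency measures are required", and gives "VLF domain (<0.04Hz) and the ultra-low frequency (ULF) domains (<0.003Hz". Appendix 1 instead defines VLF as "Absolute power of the very low frequency band (0.033 – 0.04Hz", next to LF as "Absolute power of the low frequency band (0.04 – 0.15Hz". Appendix 1 lists neither ULF nor any entropy measure.

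Section 2.1 makes the number of interpretable epochs the primary outcome. Its secondary outcomes include agreement of HRV measures between devices, and correlation of HRV with arrhythmia onset and with events such as blood-pressure variation above 20%, changes in ventilatory support and vasopressor use.

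**The concern.** An epoch fixed in time is not fixed in beats: the faster the heart, the more intervals it contains. Approximate entropy counts each template as a match to itself. That pulls the value down in short series, and the pull weakens as beats are added. The index can therefore move when heart rate moves, although the beat-to-beat dynamics are the same.

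This matters most for the event correlations in section 2.1. A 24-hour value can hardly be linked to a desaturation or a pressure drop, so the 5-minute values are the natural input. Many of the listed events can change heart rate. An association between approximate entropy and such an event could then be a heart-rate association under another name, and it would pass into the planning of the larger trial that this pilot is meant to inform.

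A smaller matter is the bottom of the spectrum. A 300-second window cannot hold one full cycle of ULF and holds very few cycles of the slowest VLF. The protocol also gives two different VLF bands.

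**Working it through.** The plan states no figure of its own on this point, so there is none to reproduce.

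**Inputs.** From the protocol: epoch length T = 300 s (section 4.3); VLF below 0.04 Hz and ULF below 0.003 Hz (section 1); VLF 0.033 to 0.04 Hz, LF 0.04 to 0.15 Hz, HF 0.15 to 0.4 Hz (Appendix 1). Assumed, because the protocol gives no values: heart rates of 60 to 120/min, template length m = 2, tolerance r = 0.2 SD, and AR(1) series as a stand-in for RR intervals.

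**1. Beats per epoch.** N = 5 × rate, so 5 × 60 = 300 and 5 × 120 = 600.

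**2. Entropy with the process held fixed.** Approximate entropy is Φ(m) − Φ(m+1), where Φ(m) is the mean over templates of the log proportion of templates within r, self-match included. Sample entropy is −ln(A/B), with A and B the matching pairs at lengths m+1 and m, self-matches excluded. With 60 simulated series per setting:

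| AR(1) coefficient | Approximate entropy, 300 beats | 600 beats | Sample entropy, 300 beats | 600 beats |
|---|---|---|---|---|
| 0.7 | 1.141 (SD 0.036) | 1.424 (SD 0.024) | 1.873 | 1.855 |
| 0.95 | 1.000 (SD 0.074) | 1.083 (SD 0.090) | 1.151 | 1.116 |

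- At 0.7 approximate entropy rises by 1.424/1.141 − 1 = 25%, which is 0.283/0.036, or about 8 epoch-to-epoch SDs. Sample entropy changes by 1.855/1.873 − 1 = −1%.
- At 0.95 the rise is 1.083/1.000 − 1 = 8% (9% in a separate run, 1.00 to 1.09), or roughly one SD. Sample entropy changes by 1.116/1.151 − 1 = −3%.
- Across coefficients the rise is 29% at 0.5, 18% at 0.85 and nil at 0.98.

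**3. Smaller rate changes.** From 80 to 88/min (400 to 440 beats), approximate entropy shifts by about 2.8% at coefficient 0.7 (about one SD) and 1.6% at 0.95 (about 0.2 SD).

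**4. Device differences.** With coefficient 0.7 and the same beats seen by both devices, 1 ms of independent timing error gives a mean paired difference of 0.002. If one series has 20% fewer beats, the difference is 0.102 at 60/min and 0.086 at 120/min.

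**5. Spectrum.** Resolution is 1/T = 1/300 = 0.00333 Hz; cycles per epoch are f × T.

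- ULF: at most 0.003 × 300 = 0.9 cycle.
- VLF read from section 1 as 0.003 to 0.04 Hz: 0.9 to 12 cycles. The share of the band with less than one cycle is (0.00333 − 0.003)/0.037 = 0.9%; with fewer than two cycles, (0.00667 − 0.003)/0.037 = 9.9%.
- VLF as in Appendix 1: 0.033 × 300 = 9.9 to 0.04 × 300 = 12 cycles, with only three frequency bins (10/300, 11/300 and 12/300 Hz).
- LF: 12 to 45 cycles. HF: 45 to 120 cycles. Both are estimable.

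**The case against.** The best reply is that the protocol names domains, not measures. It calls the epoch values short-term, gives the 24-hour recording its own long-term measures, and refers to a guideline for both. The entropy list in section 2.3 is illustrative, and sorting measures by window is ordinary SAP content. This stands in part: the absence of a per-epoch list is no fault. But section 4.3 does put the non-linear domain on each epoch, section 2.3 does name approximate entropy, and nothing removes it from the epochs.

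It is also fair that a doubling of heart rate is a large contrast, that strongly correlated series show little or no effect, and that removal of ectopic beats with interpolation limits differences in beat count. These points reduce the size of the concern but do not remove it. Interpolation of ectopic beats does not clearly cover lost signal.

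A reader might infer more than the documents support:

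- *Every spectral and non-linear measure on the epochs is unsound.* LF, HF and sample entropy up to coefficient 0.95 held up. Nothing here shows a fault in SD1 or SD2, and detrended fluctuation analysis was not tested.
- *VLF cycles are longer than the epoch.* That is true of 0.9% of the band implied by section 1 and of none of the Appendix 1 band. It fits ULF.
- *Per-epoch VLF agreement between devices would be mostly noise.* Both devices record the same heart over the same epoch, so error from few cycles is largely shared and cancels in the paired difference.
- *Approximate entropy must correlate with the events.* It can, but the size depends on the rate change and on how strongly the intervals are correlated.

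**Conclusion.** The point holds for one index. Followed as written, the plan lets heart rate move approximate entropy on 5-minute epochs without any change in dynamics: about 18 to 29% for a doubling from 300 to 600 beats at AR(1) coefficients 0.85 to 0.5, about 9% at 0.95 and none at 0.98. These sizes rest on assumed entropy settings and simulated AR(1) series; the documents supply neither settings nor RR data. Sample entropy avoids most of this up to 0.95, and no claim is made for it at 0.98.

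What is exposed is the set of secondary correlations between approximate entropy and clinical events. Device agreement is affected only where the two devices keep different numbers of beats. The primary outcome, a count of interpretable epochs, is untouched.

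Two spectral points stand beside it: ULF and the lowest VLF cannot be usefully estimated from 300 s, and section 1 and Appendix 1 disagree on the lower edge of VLF by a factor of 0.033/0.003 = 11. The documents do not show which edge is intended. Overall severity is minor.

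**What to change.** - In sections 4.3 and 2.3, use sample entropy for the 5-minute epochs. If approximate entropy is kept there, compute it on a fixed number of beats, the same for every epoch and both devices.
- Take ULF and the lowest part of VLF only from the 24-hour recordings.
- Reconcile the VLF band in section 1 with the one in Appendix 1, and use a single definition throughout.

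The cost is a few lines of protocol text and a setting in the analysis program. The downside is slightly fewer measures per epoch. A fixed beat count would also leave some beats of faster epochs unused.
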